5.2 Efficacy Assessments

[REDACTED]

The image consists of several thick, black horizontal bars of varying lengths. The top bar is the longest, followed by a shorter one below it. To the right of these, there is a large, dark, irregular shape that tapers to the right. To the left of this large shape, there is a smaller, dark, irregular shape. The entire image is set against a white background.

5.2.4 Patient Completed Efficacy Questionnaires

When these assessments are required at the times outlined in [Table 1](#), they should be the first tasks done at any visit, and prior to study medication dosing.

Patients will be provided a quiet, private place to complete the assessments. Patients will be instructed to answer all the questions to the best of their ability and without help from others (study staff, family, or friends). The study staff should review the questionnaires after they are completed and encourage patients to complete any missing information. Patients can refrain from answering any question. Study staff will record the refusal of patients to answer any question in the source documents.

A large black rectangular redaction box covers the majority of the page content. A small white rectangular box is located at the bottom center, and a white 'L' shape is in the bottom right corner.

The image consists of a series of horizontal bars of varying lengths, primarily black on a white background. There are several black bars of different widths at the top. In the middle section, there is a long black bar with a shorter black bar positioned below its right end. The bottom section features a very long black bar with a shorter black bar below its right end. On the far right side of the image, there are several white bars of varying widths, which appear to be the right-hand portions of the bars from the left side. The entire image is rendered in a high-contrast, black-and-white pixelated style, suggesting it is a scan of a document or a specific type of data visualization.

5.2.5 Physician Completed Efficacy Questionnaire

When this assessment is required at the times indicated in [Table 1](#), it should be one of the first assessments done at the visit, and must be completed prior to drug dosing.

5.2.6 *High Sensitivity C-reactive Protein*

Blood samples for evaluation of hsCRP will be collected at the times specified in [Table 1](#). Samples will be shipped to a central laboratory. Specific instructions for collection,

processing, storage and shipment of samples for hsCRP will be provided in a separate laboratory manual.

5.3 Safety Assessments

5.3.1 *Adverse Events*

AEs will be followed, recorded, and reported in line with the procedures described in [Section 7](#).

5.3.2 *Clinical Laboratory Evaluations*

Laboratory assessments will be performed by a central laboratory. Blood and urine samples will be collected at the times indicated in [Table 1](#). On dosing day(s), sampling for the analysis of clinical laboratory parameters will be performed before the administration of study medication.

Unless indicated otherwise, all laboratory samples will be processed and shipped to the central laboratory, as described in the central laboratory manual. The central laboratory will analyze the samples or send them to reference laboratory(ies) for analysis, as indicated in the manual. Refer to the central laboratory manual for the maximum total volume of blood to be collected per patient throughout the study.

The following parameters will be assessed:

Hematology: hemoglobin, hematocrit, red blood cells, platelets, total WBC count, differential WBC count, and ANC

Coagulation: INR, partial thromboplastin time, and prothrombin time

Biochemistry: albumin, alkaline phosphatase (ALP), ALT, amylase, AST, blood urea nitrogen (BUN), calcium, creatine phosphokinase, creatinine, hsCRP, gamma glutamyltransferase, glucose, inorganic phosphatase, lactate dehydrogenase, lipase, magnesium, potassium, sodium, chloride, bicarbonate, total bilirubin, total protein, and uric acid

Lipids: total cholesterol, high-density lipoprotein, low-density lipoprotein, and triglycerides

Urinalysis: pH, specific gravity, creatinine, glucose, bilirubin, blood, and protein

Refer to the laboratory manual for details regarding the collection, processing, and shipping of the blood and urine samples.

The investigator must review the laboratory report, document this review, and record any clinically relevant changes occurring during the study in the AE section of the eCRF. If known, the underlying etiology of the clinically relevant laboratory changes should be

reported as the AE, rather than the abnormal laboratory result itself. The laboratory reports must be filed with the source documents. Clinically significant abnormal laboratory findings are those that are not associated with the underlying disease under study, unless judged by the investigator to be more severe than expected for the patient's condition.

All laboratory tests with values considered clinically significantly abnormal during the patient's participation in the study or within 30 after the last dose of study medication should be repeated until the values return to normal, or baseline, or are no longer considered clinically significant by the investigator or medical monitor.

If such values do not return to normal/baseline within a period of time judged reasonable by the investigator, then the sponsor should be notified.

5.3.2.1 *Potential Drug-induced Liver Injury*

Hy's Law cases have the following 3 components:

1. The drug causes hepatocellular injury, generally shown by a higher incidence of ≥ 3 fold elevations above the ULN of ALT or AST than the placebo
2. Among study patients showing such aminotransferase elevations, often with aminotransferases much greater than $3 \times \text{ULN}$, one or more also shows elevation of serum total bilirubin to $>2 \times \text{ULN}$ or INR >1.5 , without initial findings of cholestasis (elevated ALP)
3. No other reason can be found to explain the combination of increased aminotransferase and total bilirubin, such as viral hepatitis A, B, or C; evidence for biliary obstruction; acute alcoholic hepatitis (recent drinking and AST $>2 \times \text{ALT}$ are supportive); recent history of severe hypotension or congestive heart failure; other underlying viral disease; pre-existing or acute liver disease; or another drug (including non-prescription products such as herbal supplements) capable of causing the observed injury

During the study, the investigator will remain vigilant for increases in liver biochemistry. The investigator is responsible for determining whether a patient meets potential drug-induced liver injury criteria at any point during the study.

In the event that a patient shows laboratory results of:

- AST or ALT:
 - $>5 \times \text{ULN}$ persisting for 2-weeks after study medication interruption or second occurrence of $>5 \times \text{ULN}$
 - $>3 \times \text{ULN}$ and (total bilirubin $>2 \times \text{ULN}$ or INR >1.5)

- >3×ULN with appearance of fatigue, nausea, vomiting, right upper quadrant pain or tenderness, fever, rash and/or eosinophilia (>5%)

Please refer to [Appendix 1 Possible Hy's Law Liver Chemistry Action and Follow-up Assessments](#) for further information.

5.3.3 *Pregnancy*

All patients are required to meet the requirements relating to pregnancy and use of contraception described in the inclusion and exclusion criteria (see [Section 4.1](#) and [Section 4.2](#), respectively).

Serum beta human chorionic gonadotrophin (β-hCG) testing will be performed for female patients of childbearing potential at screening (within 28 days of Day -1), and a urine pregnancy test will be performed on Day 1 (prior to dosing) and throughout the study.

The pregnancy test must be negative for the patient to be eligible. The serum pregnancy tests will be analyzed by the central laboratory, and the urine pregnancy tests will be analyzed locally.

Monitoring for pregnancies in female patients will continue from the patient's inclusion in the study until the follow-up visit. Male patients will be required to inform the investigator if their partner becomes pregnant during the study. The investigator should inform the sponsor within 24 hours of learning of the pregnancy or partner pregnancy by completing and submitting a pregnancy report form to the sponsor (or designee).

If a patient becomes pregnant, study medication will be permanently discontinued and she will be withdrawn from the study after completing the assessments planned for the end of study visit 8 (see [Table 1](#)). Any pregnant patient and the fetus will be closely followed up throughout the duration of the pregnancy to determine the outcome (including spontaneous miscarriage, elective termination, normal birth, or congenital abnormality). The investigator will ask the patient to provide informed consent to record information on the health of the baby. Generally, follow-up will be required for no longer than 6 to 8 weeks beyond the estimated delivery date.

While pregnancy itself is not considered to be an AE or SAE, any pregnancy complication or elective termination of a pregnancy for medical reasons will be reported as an AE or SAE. Abnormal pregnancy outcomes (e.g., spontaneous abortion, fetal death, stillbirth, congenital abnormalities, ectopic pregnancy) will be considered SAEs.

For any male study patient whose partner becomes pregnant, the investigator will attempt to collect pregnancy information on the male patient's partner while the male patient is in this study.

The investigator will record pregnancy information on the appropriate form and submit it to the sponsor within 24 hours of learning of the partner's pregnancy. The investigator will obtain informed consent from the female partner to collect information about the pregnancy and its outcome. Information on the status of the pregnant partner and the fetus will be forwarded to the sponsor. Generally, the follow-up will be no longer than 6 to 8 weeks following the estimated delivery date. Any termination of the pregnancy will be reported regardless of fetal status (presence or absence of anomalies) or indication for the procedure. Abnormal pregnancy outcomes (e.g., spontaneous abortion, fetal death, stillbirth, congenital abnormalities, ectopic pregnancy) will be considered SAEs.

5.3.4 *12-lead Electrocardiogram*

12-lead ECG will be obtained as outlined in [Table 1](#) using an ECG machine that automatically calculates the heart rate and measures PR, QRS, QT, and QTc intervals.

The ECG tracing should clearly identify the patient, include the date and time of the assessment and the signature and date of the person who made the interpretation; the tracing will be archived at the study site. Abnormal, clinically significant ECG results will be recorded as AEs.

5.3.5 *Vital Signs*

Vital signs will be measured prior to dosing and immediately following dosing in a semi-supine position after 5 minutes' rest and will include temperature, systolic and diastolic BP, pulse, and respiratory rate. Abnormal, clinically significant vital sign results will be recorded as AEs. If known, the underlying etiology for the abnormal clinically significant vital sign will be recorded as an AE rather than the vital sign itself.

5.3.6 *Physical Examination*

The complete physical examination will include assessments of the standard physical examination items, including general appearance, skin, eyes, ears, nose, throat, head and neck, heart, chest and lungs, abdomen, extremities, lymph nodes, musculoskeletal, neurological, and other body systems, if applicable, for describing the status of the patient's health.

The brief physical examination will include, at a minimum, signs of RA.

Body weight and height (height at screening only) will also be measured and recorded. The patient should be dressed in lightweight clothing, without shoes.

Investigators should pay attention to clinical signs related to previous serious illnesses. Any new abnormalities or worsening of existing abnormalities should be reported as AEs, as appropriate (see [Section 7](#)).

A series of horizontal black bars of varying lengths, likely representing redacted text or a visual effect in a document. The bars are positioned vertically, with some having small white gaps between them and others being continuous. The lengths of the bars vary significantly, with some being very short and others extending across most of the page.

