16 APPENDICES

16.1 Appendix 1 Possible Hy's Law Liver Chemistry Action and Follow-up Assessments

Suggested Actions and Follow-up Assessments	
Actions	Follow-Up Assessments

 • Immediately discontinue study medication. • Report the event to the sponsor or designee within 24 hours. • Complete a SAE data collection tool if the event also met the criteria for an SAE.² • Perform liver chemistry follow-up assessments. • Monitor the participant until liver chemistry test abnormalities resolve, stabilize, or return to baseline (see MONITORING). • Do not restart/rechallenge participant with study treatment unless allowed per-protocol and sponsor approval is granted. • If restart/rechallenge is either not allowed per-protocol or not granted, permanently discontinue study treatment. The participant may continue in the study for any protocol-specified follow-up assessments 
MONITORING:
 
If ALT ≥ 3xULN AND bilirubin ≥ 2xULN or INR >1.5:
 
 • Repeat liver chemistry tests (ALT, AST, alkaline phosphatase, bilirubin) and perform liver event follow-up assessments within 24 hours. • Monitor participant twice weekly until liver chemistry test abnormalities resolve, stabilize, or return to baseline. • A specialist or hepatology consultation is recommended. 
If ALT ≥ 3xULN AND bilirubin < 2xULN and INR ≤ 1.5:
 
 • Repeat liver chemistry tests (include ALT, AST, alkaline phosphatase, bilirubin) and 	
 • Viral hepatitis serology³ • Obtain INR and recheck with each liver chemistry assessment until the transaminases values show downward trend • Obtain blood sample for ATI-450 drug concentration⁴ • Serum creatine phosphokinase (CPK) and lactate dehydrogenase (LDH) • Fractionate bilirubin, if total bilirubin ≥ 2xULN • Obtain complete blood count with differential to assess eosinophilia • Record the appearance or worsening of clinical symptoms of liver injury, or hypersensitivity, on the AE eCRF • Record use of concomitant medications (including acetaminophen, herbal remedies, and other over-the-counter medications) on the concomitant medications CRF 
If ALT ≥ 3xULN AND bilirubin ≥ 2xULN or INR >1.5:
 
 • Anti-nuclear antibody, anti-smooth muscle antibody, Type 1 anti-liver kidney microsomal antibodies, and quantitative total immunoglobulin G (IgG) or gamma globulins. • Serum acetaminophen adduct high performance liquid chromatography assay (quantifies potential acetaminophen contribution to liver injury in participants with definite or

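### Appendix 1 sets its liver monitoring and SAE thresholds on ALT alone, although Section 5.3.2.1 sends patients there on AST or ALT

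*Combined protocol and SAP*

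**What the plan says.** Sections 4.4.1 and 5.3.2.1 carry the same three criteria, each on AST or ALT:

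1. above 5xULN, "persisting for 2-weeks after study medication interruption or second occurrence of" that level;
2. above 3xULN together with total bilirubin above 2xULN or INR above 1.5;
3. above 3xULN with listed symptoms, rash or eosinophilia above 5%.

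In 4.4.1 they call for discontinuation. In 5.3.2.1 they refer the patient to Appendix 1. The first Hy's Law component in 5.3.2.1 also treats the two enzymes alike, describing hepatocellular injury by a higher incidence of "fold elevations above the ULN of ALT or AST than the placebo".

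Appendix 1 is a table headed "Suggested Actions and Follow-up Assessments". Its action list begins "Immediately discontinue study medication", goes on to "Report the event to the sponsor or designee within 24 hours", and directs the site to a monitoring block. The first monitoring row there opens "If ALT ≥ 3xULN AND bilirubin ≥ 2xULN or INR >1.5". The second covers ALT at or above 3xULN without a rise in bilirubin or INR. The follow-up column repeats the first condition before its extra tests. Footnotes 1 and 2 set further ALT thresholds, and footnote 2 makes the cases it describes mandatory SAEs. AST appears in the appendix only as one of the tests to repeat.

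**The concern.** The referral and the destination do not use the same enzymes. A patient can qualify for Appendix 1 on AST and then find no condition in it that fits. Such a patient is left without a stated repeat interval, monitoring frequency or extended work-up, and without the automatic SAE classification.

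This matters because safety is the primary objective and SAEs are counted in the primary endpoint. All patients also take MTX, and Section 7.2.2 requires the investigator to weigh concomitant therapy and other causes. Whether a case of possible severe liver injury is an SAE by rule, or only by judgment under Section 7.1.2, should not turn on which transaminase rose further.

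**Working it through.** The plan gives no figure to reproduce, so the check is a trace through the text.

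**Illustrative patient (assumed values).** AST 6xULN, ALT 2xULN, total bilirubin 2.5xULN with more than 35% direct, INR not above 1.5, no listed symptoms, first occurrence.

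**Entry.** Criterion 2 of 5.3.2.1 asks for AST or ALT above 3xULN and bilirubin above 2xULN. AST is 6 > 3 and bilirubin is 2.5 > 2, so the patient enters Appendix 1. The same values require discontinuation under 4.4.1.

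**Inside Appendix 1.** The six readable conditions that set a transaminase threshold are below. The last column exchanges the enzymes (ALT 6xULN, AST 2xULN) and changes nothing else.

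| Condition | What it sets | AST-led | ALT-led |
|---|---|---|---|
| Monitoring row 1: ALT ≥3xULN with bilirubin ≥2xULN or INR >1.5 | repeat and follow-up within 24 hours, then twice-weekly tests | no (2 < 3) | yes |
| Monitoring row 2: ALT ≥3xULN, bilirubin <2xULN, INR ≤1.5 | repeat within 24 to 72 hours, then weekly tests | no (2 < 3) | no (bilirubin 2.5) |
| Extra follow-up row: same condition as row 1 | autoimmune antibodies, IgG, acetaminophen adduct assay | no (2 < 3) | yes |
| Footnote 1: ALT ≥3xULN and bilirubin ≥2xULN | stop drug if bilirubin cannot be fractionated promptly | no (2 < 3) | yes |
| Footnote 2, first limb: ALT ≥3xULN, bilirubin ≥2xULN, >35% direct | mandatory SAE | no (2 < 3) | yes |
| Footnote 2, second limb: ALT ≥3xULN and INR >1.5 | mandatory SAE | no (2 < 3) | no (INR) |

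All 6 conditions name ALT and 0 name AST. The AST-led patient meets 0 of 6. The ALT-led patient with the same values meets 4 of 6.

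**General result.** Each condition requires ALT at or above 3xULN. Any patient who enters on AST with ALT below 3xULN therefore meets 0 of 6, whichever criterion opened the appendix. For an AST-led entrant with symptoms but normal bilirubin and INR, the row that fails to open is the second.

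**What the AST-led patient still receives.** Drug stops and the sponsor is told within 24 hours. The general follow-up list applies (viral serology, INR, CPK and LDH, bilirubin fractionation, blood count), and monitoring continues until resolution. The losses are the repeat deadline, the testing frequency, the extra tests and the SAE rule.

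**The case against.** **The consequence is small.** Drug is stopped, the 24-hour sponsor report has the same deadline as an SAE under Section 7.4, and Section 7.1.2 allows the case to be called an important medical event. The sponsor reviews unblinded safety data about weekly, and the table is only suggestive by its heading. This stands, and it limits the size of the point. It does not supply the missing interval. Footnote 2 is worded as an obligation despite the heading.

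**ALT alone may be a deliberate choice for specificity.** Section 5.3.2.1 lists AST above twice ALT as supporting alcoholic hepatitis, and in the example AST is three times ALT in ULN multiples (6/2 = 3). The documents do not state such a choice, however, and the referral criteria already admit AST. That remark on AST sits in a list of alternative causes to be ruled out, which is a reason to do the work-up.

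**The table may be incomplete as read.** Footnote 1 has no visible marker in the appendix body. The count of six is therefore of readable conditions.

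**A stronger reading to resist.** A reader might infer that a first, isolated AST or ALT above 5xULN has no timed work-up, since it meets none of the three criteria and Section 5.3.2 says only that clinically significant values "should be repeated until the values return to normal, or baseline, or are no longer considered clinically significant by the investigator or medical monitor". The documents do not support that conclusion. The first criterion presupposes an interruption step, and Section 6.10 records dosing delays. The section between 6.5 and 6.7 is blacked out, and the safety management plan cited in Section 3.1 is not supplied. A retest rule may be in either. Nor does the appendix's instruction to stop drug at once overreach: through 5.3.2.1, every entrant has already met a stop criterion.

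**Conclusion.** The mismatch is real. The plan refers patients on AST or ALT and then manages them by ALT alone. An AST-led entrant with ALT below 3xULN meets none of the six readable conditions, so the timed repeat, monitoring frequency, extra tests and mandatory SAE rule do not reach that patient.

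The effect is modest. It leaves the stopping decision and the 24-hour sponsor report intact, and it does not touch sample size or the planned analysis methods. It can affect whether a case is classified as an SAE. With about 25 patients planned, one such case is 1/25 = 4% of those enrolled. The documents give no rate for these elevations and none is assumed.

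The conclusion rests on the readable text of 4.4.1, 5.3.2.1 and Appendix 1. It does not depend on any redacted section.

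**What to change.** In Appendix 1, replace ALT with *ALT or AST* in each of the six threshold conditions: both monitoring rows, the extra follow-up row, footnote 1 and both limbs of footnote 2. The numerical thresholds can stay as they are.

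The drafting cost is a few words. In conduct, AST-led patients would have a few more liver tests, and those with a qualifying bilirubin or INR rise would generate SAE reports. Some of these cases will prove to be muscle- or alcohol-related. The CPK already on the follow-up list helps to identify a muscle source, and those with a qualifying bilirubin or INR rise already stop drug under 4.4.1.

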3 STUDY PLAN

3.1 Overall Study Design and Plan

The study visit schedule and planned assessments at each visit are detailed in [Table 1](#).

This is a Phase 2a, randomized, investigator- and patient-blind, sponsor-unblinded, parallel group, placebo-controlled study to investigate the safety, tolerability, PK, and PD of ATI-450 plus MTX versus MTX alone in patients with moderate to severe RA.

Approximately 25 patients are planned to be enrolled with the expectation that at least 15 patients will complete the 12-weeks of treatment. The study will consist of an up to 28-day screening period, a 12-week treatment period, and a 4-week follow-up period. The total duration of the study for patients remaining in the study until their final follow-up assessment will be up to 20 weeks.

The investigator will obtain signed informed consent from the patient before any study procedures are performed. For further details regarding the informed consent process, see [Section 9.3](#).

During the screening period each patient will be required to have all assessments performed as outlined in the Schedule of Assessments ([Table 1](#)). The MRI is not to be performed until the site obtains the results of the patient's hsCRP level to ensure that this assessment meets entry criteria prior to performing the MRI. The patient will have the RAMRIS Hand-Wrist assessment performed at their local institution and evaluated by a central radiology review team to determine if they meet the radiological inclusion criteria. Results for all of the screening assessments must be available at the time patient eligibility is reconfirmed prior to randomization and dosing.

Patients whose eligibility is confirmed at baseline will be randomized in a 3:1 ratio to receive either ATI-450 tablets (50 mg BID) plus MTX, or matching placebo tablets plus MTX. Study medications will be administered orally for 12 weeks. Patients will be required to remain on a stable dose of MTX (7.5 mg to 25 mg/week) and a stable dose of folic or folinic acid (≥ 5 mg/week) for the duration of the study.

Patients will attend clinic visits on Days 7, 14, 28, 42, 56, and 84 (± 1 day) for safety, efficacy, PK, and PD assessments. The morning dose of study medication will be administered in the clinic on each study visit day.

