After 4 weeks of treatment (Day 28), each patient's safety data (e.g., AEs, laboratory values, vital signs, ECGs) will be reviewed by the Aclaris medical monitor and the Aclaris safety physician to ensure that the patient is tolerating the treatment regimen and is deemed suitable to continue treatment for the next 8 weeks. This review is described in more detail in the study-specific safety management plan.

End of study assessments will be conducted on Day 84 (Week 12). A safety follow-up visit will be conducted 30 days (+7 days) after the last dose of study medication.

The study is randomized and blinded to the investigator, patient, site personnel and Aclaris clinical monitors involved in site and patient monitoring with regard to ATI-450 and placebo to prevent bias in treatment allocation and in the assessment of treatment effect. See [Section 6.2](#) for details on access to the treatment codes in the event of emergency unblinding. The Aclaris statistician, medical and safety monitor will be unblinded to each patient's treatment assignment.

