3.3 End of Study

A patient is considered to have completed the study if he/she has completed all study visits. The end of the study is defined as the date of the last visit or date of last procedure of the last patient in the study.

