4.1 Inclusion Criteria

The following inclusion criteria must be met for a patient to be eligible for inclusion in the study:

1. Able to comprehend and be willing to sign the Institutional Review Board (IRB) approved subject informed consent form (ICF) prior to the administration of any study-related procedures.
2. Diagnosis of adult-onset RA as defined by the 2010 American College of Rheumatology/European League Against Rheumatism (ACR/EULAR) classification criteria.
[REDACTED]
3. [REDACTED]
4. [REDACTED]
5. [REDACTED]
6. Patients must have definitive intra-articular synovitis or osteitis defined as a score of 1 or greater on a Hand-Wrist MRI as assessed by central imaging reader (using RAMRIS).
7. On a stable MTX dose (defined as 7.5 mg to 25 mg weekly) and a stable dose of folic or folinic acid (defined as \geq 5mg/week) for at least 4 weeks prior to the screening visit.
8. Male or non-pregnant, non-nursing female patients between 18 and 70 years of age, inclusive.
 - Female patients that are of childbearing potential must use 2 methods of highly effective contraception* - one of which must be a physical barrier for the duration of the study and for 30 days after the last dose
 - Male patients of childbearing potential with a female partner of childbearing potential must agree to use a condom plus another highly effective form of birth control for the duration of the study and for 90 days after the last dose
9. Female patients must have a negative serum pregnancy test at screening and a negative urine pregnancy test prior to dosing on Day 1.
10. Screening laboratory evaluations (hematology, chemistry, coagulation, and urinalysis) must fall within the normal range of the central laboratory's reference ranges unless the results have been determined by the investigator to not be clinically significant.
11. Willing and capable of taking appropriate coronavirus disease 2019 (COVID-19) risk mitigation precautions (e.g., wearing a mask in public, adhering to social

distancing, etc.) as recommended or required by local, state, or federal guidelines during participation in the study.

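### Male patients must use contraception for 90 days after the last dose, but their stated duty to report a partner pregnancy covers only one that begins during the study

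*Combined protocol and SAP*

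**What the plan says.** Four parts of the protocol bear on this.

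- **Contraception.** Criterion 8 in Section 4.1 asks a male patient with a partner of childbearing potential to use a condom plus a second highly effective method "for the duration of the study and for 90 days after the last dose".
- **The patient's duty to report.** Section 5.3.3: "Male patients will be required to inform the investigator if their partner becomes pregnant during the study".
- **The investigator's duties.** The same section says that "The investigator should inform the sponsor within 24 hours of learning of the pregnancy or partner pregnancy", and repeats for partners that "The investigator will record pregnancy information on the appropriate form and submit it to the sponsor within 24 hours of learning". Neither sentence has an end date. The section also provides for the partner's consent and for follow-up to six to eight weeks past the due date. One sentence, however, has the investigator try to collect partner information only "while the male patient is in this study".
- **The end of participation.** Section 3.1: "A safety follow-up visit will be conducted 30 days (+7 days) after the last dose of study medication". Section 3.3: "A patient is considered to have completed the study if he/she has completed all study visits".

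**The concern.** The sponsor chose 90 days as the period in which a male patient should avoid fathering a child. A contraceptive failure in that period is the event the precaution is meant to prevent, so the sponsor would want to hear of it. Yet the sentence that tells the patient to speak up is tied to the study, and his last scheduled visit comes well before day 90. The 24-hour report to the sponsor starts only when the investigator learns of the pregnancy. If nobody has asked the patient to say anything, that report may never be triggered.

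The provisions for women do line up. Their contraception runs to 30 days after the last dose, and pregnancy monitoring runs to the follow-up visit at 30 to 37 days. For men the contraception period after the last dose is three times as long, with no matching extension of the reporting duty.

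What is at stake is the completeness of the reproductive-safety record. Partners are not in the Safety population, and the window for treatment-emergent events closes at the last follow-up visit or 30 days after the last dose, whichever is later. No endpoint or planned analysis depends on this.

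**Working it through.** The protocol gives no figure for this gap, so there is none to reproduce. The check is a count of days.

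**Inputs**
- End of male contraception: day 90 after the last dose (Section 4.1, criterion 8).
- Last scheduled visit (Visit 9): day 30 to day 37 after the last dose (Section 3.1).

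**Which pregnancies the sentence covers.** The time limit attaches to when the partner becomes pregnant, not to when the pregnancy is noticed. One that begins before participation ends but is recognised later is still covered. Only pregnancies that begin afterwards fall outside.

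**Reading 1: the study is the patient's own participation.**
Gap = 90 − (days from last dose to Visit 9)
- Visit 9 on day 37: 90 − 37 = 53 days; 53/90 = 58.9%
- Visit 9 on day 30: 90 − 30 = 60 days; 60/90 = 66.7%

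Three things support this reading. Criterion 8 names the duration of the study and the 90 days as separate periods. Section 5.3.3 itself uses the words "while the male patient is in this study". Section 3.1 gives duration per patient: "The total duration of the study for patients remaining in the study until their final follow-up assessment will be up to 20 weeks".

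**Reading 2: the study is the whole trial.** Sections 3.3 and 14 define the end of the study by the last patient.
Gap = max(0, 90 − days from the patient's last dose to the end of the trial)
- Last dose at least 90 days before the trial ends: 0 days
- Last patient to finish, with Visit 9 on schedule: again 90 − 37 = 53 to 90 − 30 = 60 days

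**Comparison with women.**
Gap = max(0, 30 − days from last dose to Visit 9)
- Visit 9 on day 30: max(0, 30 − 30) = 0 days
- Visit 9 on day 37: max(0, 30 − 37) = 0 days

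**After the fix.** With the male reporting duty running to day 90, the gap is 90 − 90 = 0 days on either reading.

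A patient who stops drug early or leaves before Visit 9 will have a different gap. The protocol does not fix when his last contact would be, so I give no figure. Nor does it give the number of men with partners of childbearing potential, so I estimate no event count.

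**The case against.** The best case against the point has four parts.

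1. **No rule is broken.** Nothing in the protocol says that the reporting and contraception periods must match, and the 90 days are written as a precaution, not as a surveillance window. This stands. The point is an improvement, not an error or a contradiction.
2. **The instruction may be in the consent form.** That is a natural place for a duty on the patient, and the consent pages were not available. This also stands: the finding is limited to the protocol text that can be seen.
3. **The phrase is undefined and the explicit end-of-study definitions are trial-wide.** This stands in part. The patient-level reading is the better supported, but it is not established. Even on the other reading a gap remains for men who finish near the end of the trial, and a man's duty would then depend on when other patients finish.
4. **The investigator's side is already covered.** This largely stands. A reader might infer that reporting to the sponsor, or collection of partner information, stops when the patient leaves the study. The documents do not support that. The 24-hour report is open-ended, and follow-up past the due date could hardly fit within about 20 weeks of participation, so the sentence limiting collection cannot sensibly end it. Section 7.3 relieves investigators of actively seeking events after participation. It also requires them to notify the sponsor promptly of any serious event that they learn of later and consider reasonably related, and Section 5.3.3 counts abnormal partner-pregnancy outcomes as serious.

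All of these safeguards, however, need the site to know of the pregnancy. None asks the patient to tell it.

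**Conclusion.** The point holds as a minor gap in the patient's own instruction. On the patient-level reading, with Visit 9 on schedule, a partner pregnancy beginning in the last 53 to 60 of the 90 days (58.9% to 66.7%) carries no stated duty on the male patient to report it. On the trial-wide reading the gap runs from 0 days to the same 53 to 60 days, depending on when he finishes relative to the last patient.

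A reader might go further and infer that exposure pregnancies will be lost in practice. The documents do not show this: a patient may volunteer the information, and the consent form may ask for it. With about 25 patients and two contraceptive methods required, few events are expected.

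**What to change.** Make two edits in Section 5.3.3.

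- **Reporting sentence.** Require male patients to inform the investigator if their partner becomes pregnant during the study or within 90 days after the last dose of study medication.
- **Collection sentence.** Apply that same period to when the pregnancy begins, and delete the limit "while the male patient is in this study". Putting a 90-day limit on the collection itself would not do, because it would cut across the follow-up past delivery that the section already allows.

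Mirror the instruction in the consent form if it is not already there. The investigator's 24-hour duty needs no change.

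The cost is two sentences and perhaps one line of consent text. Passive reporting is enough, and no visit is added. The downside is that sites keep a reporting route open for about two more months after each male patient's follow-up visit.
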